9.2.1.2. Sensitivity Analysis for the Primary Endpoint

Statistical Analysis Plan

Mitsubishi Tanabe Pharma America, Inc.

9.2.1.3. Additional Supportive Analysis for the Primary Endpoint

9.2.1.3.1. Supportive analysis will be done for the Secondary Estimand

The ICEs will be addressed as follows:

- For subjects without the ICE of AMX0035 treatment (ICE1) and early discontinuation (ICE2), all post-randomization ALSFRS-R data until Week 48 will be included.
- For subjects with either ICE1 (additional/new AMX0035 treatment), ICE2 (early discontinuation), or both, only ALSFRS-R observations prior to the first ICE occurrence will be included.

Following the implementation of the above rules and assuming MAR for all missing data, the primary analysis model will be repeated.

9.2.1.4. Key Secondary Analyses

The key secondary endpoints will be inferentially analyzed in the pre-specified order to maintain the overall Type I error.

9.2.1.4.1. %Slow Vital Capacity (%SVC) Change from Baseline to week 48

The first Key secondary endpoint is %SVC change from baseline to week 48. This endpoint analysis will be performed on the FAS. All available %SVC data regardless of use of additional/new AMX0035 treatment (ICE1) drug and all available % SVC data up to early

Statistical Analysis Plan
Protocol No. MT-1186-A02

Mitsubishi Tanabe Pharma America, Inc.

discontinuation (ICE2) will be included.

The changes from baseline to all post-baseline visits until week 48 in %SVC will be estimated using a MMRM using SAS PROC MIXED. The model includes response data from all post-baseline visits with no imputation for missing data. The %SVC at baseline, randomization strata of ALSFRS-R rate of decline score during the screening period (2 levels strata of -1,-2 or -3,-4), Geographical Region (3 levels strata of Europe, America or Asia Pacific), Treatment Group, Visit and Treatment-by-Visit interaction will be included as fixed factors in the model. An unstructured covariance structure will be assumed and the denominator degrees of freedom will be computed using the Kenward-Roger method. In case the model will not converge with the unstructured covariance structure, the heterogeneous compound symmetry and the heterogeneous Toeplitz structure will be used instead (in that order). The least-squares mean (LSMEANS) estimates for the mean change from baseline to weeks 48 as well as the difference of the estimates between oral edaravone 105 mg daily versus oral edaravone 105 mg on/off regimen will be displayed with their corresponding standard errors, p-values, and 95% CI.

9.2.1.4.2. ALSAQ40 Change from Baseline to week 48

The second Key secondary endpoint is ALSAQ40 change from baseline to week 48. All available ALSAQ40 data regardless of use of additional/new AMX0035 treatment (ICE1) drug and all available ALSAQ40 data up to early discontinuation (ICE2) will be included for the second key secondary analysis. The analysis of this endpoint will be performed using the FAS and will use the same methodology as described for the 1st Key Secondary endpoint replacing the %SVC at baseline covariate with ALSAQ40 at baseline. The LSMEANS estimates for the mean change from baseline to weeks 48 as well as the difference of the estimates between oral edaravone 105 mg daily versus oral edaravone 105 mg on/off regimen will be displayed with their corresponding standard errors, p-values, and 95% CI.

[REDACTED]

[REDACTED]

[REDACTED]

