2. INTRODUCTION

This statistical analysis plan (SAP) is based on the final global protocol (v5.0) dated 22-Sep-2022. The plan covers statistical analysis, tabulations and listings of the study data to evaluate and compare the efficacy, safety and tolerability of Oral edaravone 105 mg administered once daily to Oral edaravone 105 mg administered in cycles of ‘on/off’¹ in subjects with ALS over 48 weeks. The structure and content of this SAP provides sufficient details to meet the requirements identified by the FDA and International Conference on Harmonization of Technical Requirements for Registration of Pharmaceuticals for Human Use (ICH): E9 Guidance on Statistical Principles in Clinical Trials. All work planned and reported for this SAP will follow internationally accepted guidelines, published by the American Statistical Association, and the Royal Statistical Society, for statistical practice.

¹ 14 days, followed by placebo for 14 days and subsequently, repeat oral edaravone 105 mg administered for 10 days followed by placebo for 18 days

Statistical Analysis Plan
Protocol No. MT-1186-A02

Mitsubishi Tanabe Pharma America, Inc.

The following documents were reviewed in preparation of this SAP:

- Clinical Study Protocol MT-1186-A02 Version 5.0
- Case report form (CRF) for MT-1186-A02
- Standard Operating Procedure (SOP) GLB-BST-SOP002 for Statistical Analysis Plan
- ICH E9 Guidance on Statistical Principles for Clinical Trials.
- ICH E3 Structure and Content of Clinical Study Reports (CSRs)
- ICH E14 (may, 2005) clinical evaluation of QT/QTC interval prolongation

Any statistical analysis details described in this document supersede the description of statistical analysis in the protocol. In case of major differences, e.g. changes in the analysis related to the primary endpoint, a protocol amendment will be considered. The SAP may be updated during the study conduct and will be finalized before final database lock. Any deviations from the planned analysis will be described and justified in the CSR.

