7.3. Type I Error Control

The family-wise type I error of 5% will be maintained for the primary endpoint and key secondary endpoints. To control the overall type I error rate for multiple comparisons across the primary endpoint and the key secondary endpoints, the fixed sequence procedure will be applied. The testing order are described in section 9.2.1.4

Denote:

- H_0x as the null hypothesis to be rejected for each analysis.
- Edaravone 105 mg oral dose once daily for 48 weeks as Treatment group 1
- Edaravone 105 mg oral dose on/off as Treatment group 2

1. H_{01} : There is no treatment difference between Treatment Group 2 and Treatment Group 1 in CAFS at Week 48
2. H_{02} : There is no treatment difference between Treatment Group 2 and Treatment Group 1 in change from baseline to Week 48 in %SVC
3. H_{03} : There is no treatment difference between Treatment Group 2 and Treatment Group 1 in change from baseline to Week 48 in ALSAQ40
4. H_{04} : There is no treatment difference between Treatment Group 2 and Treatment Group 1 in time to death, tracheostomy, or permanent assisted mechanical ventilation (≥ 23 hours/day)
5. H_{05} : There is no treatment difference between Treatment Group 2 and Treatment Group 1 in time to death or permanent assisted mechanical ventilation (≥ 23 hours/day)
6. H_{06} : There is no treatment difference between Treatment Group 2 and Treatment Group 1 in time to death

Hypothesis H_{01} for the primary analysis will be tested at a significance level of 5%. In order to protect the study from type-I error inflation, the first key secondary endpoints will be interpreted inferentially only if H_{01} is found significant. Type-I error will be further controlled

for the key secondary endpoints (H02 – H06) when each will be analysed only in case the preceding endpoint will have a p-value less or equal to 0.05.

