8.4.2. Efficacy Measures

8.4.2.1. Combined Assessment of Function and Survival Score (CAFS)

CAFS ranks patients' clinical outcomes based on survival time and change in the ALSFRS-R score¹⁰.

CAFS Scoring:

To calculate a patient's CAFS, each patient is compared individually to all other patients in the study. The summary score for each patient is the sum of the comparisons (1, 0, 1) against all other patients (Figure 2). For each pairwise comparison of patients, the patient who fares better earns a point, and the one who fares worse loses a point. In the case of a tie, no points are added or subtracted. If both participants die, the one surviving longer fared better; if only one survives then that patient fared better; and if both participants survive, the one with the smaller decline in ALSFRS-R from baseline to week 48 fared better. If a participant discontinues early or ALSFRS-R at week 48 are missing, the participant will be treated as alive at week 48 and the ALSFRS-R at week 48 will be imputed missing using multiple imputation under missing mechanism assumption.

CAFS Ranking:

Next, patients' summary scores are ranked (Figure 3). In general, the ranking has the following characteristics:

- (1) The first patient who dies will have the lowest score and is ranked the lowest;
- (2) the last to die is ranked above all others who die;

- (3) Among survivors, the patient with the greatest decline in ALSFRS-R is ranked just above the last patient who died;
- (4) The surviving patients with the least decline in ALSFRS-R is ranked highest.

[REDACTED]

[REDACTED]

The average rank score is then calculated for each treatment group. A higher mean rank score indicates that participants in that treatment group, on average, fared better.

Figure 2: [REDACTED]

8.4.2.2. %Slow Vital Capacity (%SVC) Change from Baseline at week 4, 8, 12, 24, 36 and 48

SVC measurements will be conducted in clinic at around the same time of day where possible with the subject in sitting upright position. Subjects should make at least 3 attempts to generate acceptable and reproducible SVC data. If subjects cannot complete all three attempts due to disease progression or other reasons, it will not be considered a protocol deviation. The best value will be selected and will be recorded in the eCRF.

8.4.2.3. ALSAQ40 Change from Baseline at week 24 and 48

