9.2.1.5. Other Secondary Efficacy Analyses

All available data regardless of use of additional/new AMX0035 treatment (ICE1) drug and all available data up to early discontinuation (ICE2) will be included. For analysis of King's ALS Clinical Stage, if death after early discontinuation (ICE2) was occurred, the death event will be included.

9.2.1.5.1. Changes from baseline in ALSFRS-R score at Weeks 4, 8, 12, 24, 36 and 48

The Change from baseline in ALSFRS-R score at Weeks 4, 8, 12, 24, 36 and 48 will be analyzed using the similar model as specified for the 1st key secondary analysis replacing the %SVC at baseline covariate with ALSFRS-R at baseline. The LSMEANS estimates for the mean change from baseline to Weeks 4, 8, 12, 24 and 36 and 48, as well as the difference of the estimates between oral edaravone 105 mg daily versus oral edaravone 105 mg on/off regimen will be displayed with their corresponding standard errors, p-values, and 95% CI. This endpoint will be analyzed using the FAS. The same analysis will be performed for ALSFRS-R subdomains.

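### The %SVC model lets only treatment vary by visit, so a prognostic decline-rate stratum would leave the Week 48 standard error wider than necessary

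*SAP*

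**What the plan says.** SAP 9.2.1.4.1 fits change from baseline in %SVC at all post-baseline visits (Weeks 4, 8, 12, 24, 36 and 48). The covariates are baseline %SVC, the randomisation stratum for ALSFRS-R decline over the 8-week screening period (1-2 points versus 3-4 points) and region. For the remaining terms it says "Treatment Group, Visit and Treatment-by-Visit interaction will be included as fixed factors in the model". On covariance it says "An unstructured covariance structure will be assumed and the denominator degrees of freedom will be computed using the Kenward-Roger method".

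The same model serves other endpoints with only the baseline covariate exchanged. ALSAQ40 (9.2.1.4.2) "will use the same methodology as described for the 1st Key Secondary endpoint". ALSFRS-R (9.2.1.5.1) "will be analyzed using the similar model as specified for the 1st key secondary analysis". %FVC and body weight follow the same pattern in 9.2.1.5. ALSAQ40 has only two post-baseline visits; the heading of SAP 8.4.2.3 reads "ALSAQ40 Change from Baseline at week 24 and 48".

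%SVC is H02 in the fixed sequence of SAP 7.3, where for H02 to H06 "each will be analysed only in case the preceding endpoint will have a p-value less or equal to 0.05". The protocol's MMRM (17.4.5.1) has the same structure. No visible text in either document adds a stratum-by-visit or baseline-by-visit term to this model.

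**The concern.** A main-effect covariate in an MMRM has one coefficient for all visits. That is harmless if the covariate shifts every visit by the same amount. A rate-of-decline stratum is unlikely to do so: on a change-from-baseline outcome, fast and slow decliners start together and drift apart. Generalised least squares then estimates the shared coefficient mostly from the early visits, where variance is low and the gap is still small. At Week 48 the model corrects for only a fraction of the gap, and the rest counts as unexplained variance.

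Because randomisation was stratified on this factor, the arms are already balanced on it. The true spread of the treatment estimate is therefore smaller than the reported standard error, and the test is conservative. What is at stake is power for H02: a miss there closes H03 to H06. H02 is itself reached only if CAFS succeeds. ALSFRS-R by MMRM is outside the testing sequence, so there only the width of the confidence interval is affected.

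**Working it through.** **1. The plan's own figure.** SAP 4.2 gives 190 per arm, 30% dropout, difference 2.6, SD 7, two-sided 5%. Completers per arm: 190 × 0.7 = 133. SE = 7 × √(2/133) = 0.858, and 2.6/0.858 = 3.03. Power is 85.7% by the normal approximation and 85.5% by the noncentral t, so the stated 85.5% is reproduced. Neither document gives an SD, effect or power for %SVC or ALSAQ40, so these ALSFRS-R values stand in for scale.

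**2. Plausible stratum gaps (assumption).** The stratum midpoints, 1.5 and 3.5 points per 8 weeks, differ by 2 points, or 2 × 6 = 12 points over 48 weeks if fully sustained. Gaps D of 3, 4.5 and 6 points correspond to 25%, 37.5% and 50% persistence. With 40% of subjects in the fast stratum (assumption), the stratum carries 0.4 × 0.6 × D² = 0.24D² of the total variance of 49, leaving a within-stratum variance of 49 − 0.24D².

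**3. Approximate SE ratio.** In the simulation of step 4 the shared coefficient removed 6-15% of the Week 48 gap, so a fraction r of 0.85 to 0.94 remains. Ratio of planned SE to SE with stratum-by-visit ≈ √(1 + 0.24(rD)² / within variance).

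| D | 0.24D² | Share of 49 | Within variance | Ratio, r = 0.85 | Ratio, r = 0.94 |
|---|---|---|---|---|---|
| 3 | 2.16 | 4% | 46.84 | 1.017 | 1.020 |
| 4.5 | 4.86 | 10% | 44.14 | 1.039 | 1.048 |
| 6 | 8.64 | 18% | 40.36 | 1.075 | 1.090 |

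**4. Simulation of the planned model.** 380 subjects, permuted blocks of 4 within the six strata, about 30% monotone MAR dropout, unstructured covariance, 1,000 replicates. Stratum, baseline and random-slope effects were linear in time, total Week 48 SD was fixed at 7, and measurement noise was 10% or 30% of Week 48 variance. The planned SE was wider by 0%, 2%, 4-5% and 7-9% at gaps of 0, 3, 4.5 and 6 points. At 6 points:

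| Noise | Planned SE | SE with stratum-by-visit | Ratio | Empirical SD, planned model | Power, planned | Power, with term |
|---|---|---|---|---|---|---|
| 10% | 0.770 | 0.708 | 1.088 | 0.694 | 94.7% | 96.2% |
| 30% | 0.783 | 0.729 | 1.074 | 0.747 | 92.4% | 94.7% |

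The power loss is 1.5 and 2.3 points here, and 0.2 to 2.3 points over gaps of 3 to 6. Rejection under the null with the planned model was 3.5-5.3% in all scenarios (Monte Carlo error about 0.7 points), so there is no inflation. With no stratum effect both SEs were 0.776. That lies between 7 × √(2/190) = 0.718 (no dropout) and 0.858 (completers only), as expected when the MMRM uses dropouts' partial data.

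**5. Cross-check by a second simulation.** This one used maximum likelihood, z-based SEs, half the subjects in each decline stratum, dropout unrelated to outcome and 60 datasets per scenario. For gaps of 0.25, 0.5, 0.8 and 1.2 within-stratum SDs growing linearly, the SE ratios were 1.008, 1.027, 1.067 and 1.144. A constant 0.5 SD shift gave 1.0015, the same as no effect. At 1.2 SD the planned SE was 0.129 but the empirical SD of the estimate was 0.112, which again shows a conservative SE.

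**6. Two-visit endpoints and baseline.** On the ALSAQ40 schedule the shared coefficient removed 27-52% of the gap. The SE was wider by 1%, 1-3% and 3-5% at 3, 4.5 and 6 points, with 0.1 to 1.8 points of power lost. For baseline-by-visit, tested separately, a correlation of 0.2 or 0.3 between baseline and Week 48 change made the planned SE 1.6% or 4.0% wider with six visits, and 0.9% or 2.4% wider with two.

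**The case against.** The planned model is valid and is the one the protocol specified. At the worst gap shown, its SE (0.770-0.783) is still below the 0.858 implied by the sample-size calculation, so the trial is not short of its design power. Every figure is on the ALSFRS-R scale, and no passage shows that an ALSFRS-R decline stratum predicts change in %SVC or ALSAQ40, or by how much. At a 3-point gap the loss is about 2% in SE. Region is also a stratification factor and gets no visit term in the proposal. A late change to a gated endpoint departs from the protocol model and has to be recorded.

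Most of this stands as a limit on size. The loss for %SVC itself is unknown and may be small, and the planned analysis is not an error. It does not remove the point. The direction is clear whenever the stratum gap grows over time, the added term costs nothing measurable when it does not, and a comfortable margin on the ALSFRS-R scale says nothing about the margin for %SVC. The omission of region is minor: it is not a rate of decline, so there is no comparable reason to expect its effect to grow.

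**Conclusion.** The point holds, as a matter of efficiency and not of validity. If the decline-rate stratum is prognostic with an effect that grows over visits, the planned Week 48 SE for %SVC is conservative: by about 2% at a 3-point gap and 7-9% at 6 points on the ALSFRS-R planning scale. A 7-9% wider SE is equivalent to losing 1 − 1/1.07² = 13% to 1 − 1/1.09² = 16% of the information. ALSAQ40 is affected less because it has two visits.

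These sizes rest on assumed stratum gaps, stratum share, noise and linear growth, and on ALSFRS-R values in place of %SVC values. The change should be made because it is nearly free and protects the first gated secondary test, but the conclusions of the trial do not depend on it.

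**What to change.** Before unblinding, add decline-stratum-by-visit to the fixed effects in SAP 9.2.1.4.1, so that ALSAQ40, ALSFRS-R, %FVC and body weight inherit it. Add baseline-by-visit as a companion term (gain 0-4% in SE under the correlations above). Leave the rest of the model as it is.

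With six visits this adds 5 + 5 = 10 parameters, and with two visits 1 + 1 = 2, in a 380-subject model, all built from variables already in it. The SAP allows the change: "The SAP may be updated during the study conduct and will be finalized before final database lock". It also needs a line in SAP section 11, because the protocol assigns the primary's MMRM to the continuous key secondaries, and a check that the subgroup models in 9.4 stay consistent. No new data and no change to the testing sequence are needed.

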3.3.3. Other Secondary Endpoints

The following efficacy endpoints are defined as 'other' secondary:

- Change from baseline in ALS Functional Rating Scale-Revised (ALSFRS-R) score at Weeks 4, 8, 12, 24, 36, and 48
- Change from screening and baseline in % forced vital capacity (FVC) at Weeks 24 and 48
- Change from baseline in %SVC at Weeks 4, 8, 12, 24, and 36
- Change from baseline in ALSAQ40 to Week 24
- Change from baseline in body weight score at Weeks 4, 8, 12, 24, 36, and 48
- CAFS score at Weeks 24
- King's ALS Clinical Stage derived from ALSFRS-R score and death

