4. STUDY DESIGN

4.1. Study Design

This is a Phase 3b, multicenter, double-blind, parallel group, randomized, study that will evaluate the efficacy and safety of 2 treatment regimens of edaravone for a period of 48 weeks in subjects with ALS as follows:

- Group 1: Edaravone 105 mg oral dose once daily for 48 weeks
- Group 2: Edaravone 105 mg oral dose in for 14 days, followed by a 14-day placebo. Subsequently, repeat edaravone 105 mg oral dose in for 10 days followed by 18-day placebo (regimen denoted as on/off).

Eligible subjects will be randomized at baseline in a 1:1 ratio to receive 1 of 2 treatment groups. Randomization will be stratified according to ALSFRS-R rate of decline score for 8 weeks screening period (2 levels strata of -1,-2 or -3,-4) and geographical region (3 levels strata of Europe, America or Asia Pacific).

Concomitant use of riluzole is permitted when the doses and regimens will remain unchanged from the day of evaluation of ALSFRS-R at the screening visit, through the end-of-treatment (EOT) or early termination (ET). Although dose reduction, dose interruption or discontinuation due to the onset of AEs, progression of dysphagia, or gastrostomy while on oral edaravone 105 mg are allowed, it is prohibited to initiate the use of riluzole. Subjects who initiate riluzole therapy de-novo during the treatment period will be discontinued from the study. The use of AMX0035 will be allowed for patients in the event that it becomes commercially available via prescription in their respective country. AMX0035 should be taken at least 1 hour after MT-1186.

This study consists of a screening period of 8 weeks, a double blind treatment period of 48 weeks, and a safety follow-up period of 2 weeks. A schedule of assessment of all study procedures is provided in Table 1.

- **Screening period:** Screening assessments will be performed up to 8 weeks (\pm 7 days) prior to Day 1. All screening evaluations must be completed and reviewed to confirm that potential subjects meet all eligibility criteria. If a subject has not met all eligibility criteria at the end of the screening period, the subject will be registered as a screen fail. Screen fail subjects may be eligible for re-screening 1 time.
- **Double-blind Treatment Period:** Subjects who successfully complete the screening period will return to the study clinic on Day 1 in a fasting state (eg, without breakfast) and inclusion

Statistical Analysis Plan
Protocol No. MT-1186-A02

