4.2. Sample Size and Power Considerations

Assuming the use of a t-test, a 2-sided alpha level of 5% and a 30% dropout rate up to Week 48, a sample size of 190 subjects per groups (380 subjects in total) will provide 85.5% power to detect an effect size of 0.37 (ie, an absolute treatment difference of 2.6 with an associated standard deviation [SD] of 7) in the change from baseline in ALSFRS-R score to Week 48 between edaravone 105 mg oral dose once daily versus edaravone 105 mg oral dose on/off regimen; see details in Appendix 1.

A sample size of 190 subjects per groups will have 78% power to detect statistically significant result for the time to death, tracheostomy, or permanent assisted mechanical ventilation. This calculation assumed a true hazard ratio between edaravone 105 mg daily (test) to edaravone 105 mg on/off regimen (control) of $HR=0.3$. Namely, 70% reduction in the hazard assuming 90% survival rate at Week 48 for the control group. This calculation assumes 2-sided alpha of 5% using the log-rank test and follow-up time of 48 weeks.

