7.2. Statistical Tests

Unless otherwise specified, all statistical tests will be done as 2-sided at the 5% significance level. Point estimates of treatment differences will be accompanied with 2-sided 95% confidence intervals (CIs) where applicable.

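### If the unstructured %SVC model fails to converge, the SAP's structured fallback does not assure the 5% level at Week 48 (low severity)

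*SAP*

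**What the plan says.** SAP 9.2.1.4.1 models change in %SVC at all post-baseline visits with an unstructured covariance and Kenward-Roger degrees of freedom. Its only provision for non-convergence is that "the heterogeneous compound symmetry and the heterogeneous Toeplitz structure will be used instead (in that order"). The section names no robust (sandwich) variance and no other way to obtain the unstructured fit. Nothing in its text is blacked out.

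The intermediate %SVC endpoint in SAP 3.3.3 is "Change from baseline in %SVC at Weeks 4, 8, 12, 24, and 36". With Week 48 this makes six unequally spaced visits. SAP 9.2.1.5.1 says that ALSFRS-R change "will be analyzed using the similar model as specified for the 1st key secondary analysis", and 9.2.1.5.5 does the same for body weight, both at the same six visits. ALSAQ40 (9.2.1.4.2) and %FVC (9.2.1.5.2) also reuse the model, but have post-baseline data only at Weeks 24 and 48.

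On the level, SAP 7.2 states: "Unless otherwise specified, all statistical tests will be done as 2-sided at the 5% significance level". Under SAP 7.3, %SVC is H02 in a fixed sequence. It follows H01 (CAFS) and precedes H03 to H06.

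**The concern.** Kenward-Roger adjusts for estimating covariance parameters in a finite sample. It does not correct a wrong covariance structure. Heterogeneous compound symmetry imposes one correlation on every pair of visits. Heterogeneous Toeplitz imposes one per lag, yet lag 1 covers 4-week gaps (Weeks 4–8, 8–12) and 12-week gaps (Weeks 12–24, 24–36, 36–48).

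If patients decline at different rates, changes from baseline correlate weakly at early visits and strongly at late ones. Neither structure can follow that pattern. Both have a separate Week 48 variance parameter, but the likelihood trades it off against the misfitted correlations, so the fitted variance and the standard error can be wrong.

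The test at stake is the first key secondary, which opens the way to H03–H06. For ALSFRS-R change and body weight, which lie outside the type I error control, only the width of the intervals is at stake. The order also puts the more restrictive structure first.

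**Working it through.** **1. The plan's own figure.** The SAP gives no error rate for the fallback. Its nearest figure is the ALSFRS-R power in SAP 4.2, which rests on a two-sided 5% t-test with 30% lost by Week 48: "a sample size of 190 subjects per groups (380 subjects in total) will provide 85.5% power". The effect behind it is "an absolute treatment difference of 2.6 with an associated standard deviation [SD] of 7". Completers per group: 190 × 0.70 = 133. Noncentrality: 2.6 / (7 × √(2/133)) = 2.6 / 0.858 = 3.03. Noncentral t with 264 df gives 85.5%, so the figure reproduces (normal approximation 85.7%). It shows the sample size and dropout assumed, but says nothing about %SVC variability.

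**2. Where the fallback differs from unstructured.** Covariance parameters:

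| Post-baseline visits | Unstructured | Compound symmetry (CSH) | Toeplitz (TOEPH) |
|---|---|---|---|
| 6 (%SVC, ALSFRS-R, body weight) | 6×7/2 = 21 | 6+1 = 7 | 6+5 = 11 |
| 2 (ALSAQ40, %FVC) | 2×3/2 = 3 | 2+1 = 3 | 2+1 = 3 |

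With two visits all three are the same matrix, so the fallback changes nothing.

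**3. Large-sample level at Week 48.** Fit each structure to an assumed true covariance with 30% monotone dropout, completely at random. Let r be the model-based standard error divided by the true (sandwich) one. The actual level is 2[1 − Φ(1.96 r)].

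Assumed random-slope covariance: Cov(tᵢ, tⱼ) = s²tᵢtⱼ + k e² + e²·1[i=j]. Here s is the slope SD (points per week, 0.15–0.40), e the visit error SD (3–8), and k the shared error variance as a multiple of e² (0–2). All are assumptions.

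| True pattern | CSH r → level | TOEPH r → level |
|---|---|---|
| s 0.15, e 8, k 2 | 0.995 → 5.1% | 0.992 → 5.2% |
| s 0.25, e 5, k 0 | 0.950 → 6.3% | 0.905 → 7.6% |
| s 0.25, e 3, k 0 | 0.938 → 6.6% | 0.852 → 9.5% |
| s 0.40, e 3, k 0 | 0.940 → 6.6% | 0.810 → 11.2% |
| Exponential decay, correlation 0.96 per week | 1.025 → 4.5% | 1.096 → 3.2% |
| True compound symmetry | 1.00 → 5.0% | 1.00 → 5.0% |

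Over the whole random-slope grid, CSH gives 5.1–6.6% and TOEPH 5.2–11.2%. Over the exponential-decay cases, CSH gives 4.5–4.7% and TOEPH 2.8–3.2%; a variant gave 4.5% and 3.5%. Random-slope data scaled to the ALSFRS-R SD of 7 (error SD 1–3) give 5.8–6.6% and 6.8–11.5%.

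**4. Simulation of the SAP model.** REML, 380 subjects allocated 1:1 ("Eligible subjects will be randomized at baseline in a 1:1 ratio to receive 1 of 2 treatment groups"), about 31–32% dropout at random given observed data, and t with 270 df in place of Kenward-Roger.

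- Random slopes, error SD 5, 1,500 runs: unstructured 63/1500 = 4.2%; CSH 89/1500 = 5.9%; TOEPH 130/1500 = 8.7%. The Monte Carlo standard error at 5% is √(0.05 × 0.95/1500) = 0.6 points. The two batches pooled here were noisy (unstructured 6.0% in 500 runs, 3.3% in 1,000), but the ordering was the same in both.
- Fitted Week 48 SD in those runs: 17.9 unstructured (the true value), 16.4–16.5 CSH, 14.8–14.9 TOEPH.
- Exponential decay, 1,000 runs: unstructured 4.4%, CSH 4.1%, TOEPH 2.6%. Fitted Week 48 SD: 17.7, 20.4 and 20.3.
- The unstructured fit gave usable estimates in every run, though from good starting values.

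**5. Family-wise error.** If H01 is true, any false rejection in the sequence requires rejecting H01 first. The family-wise rate is then at most the level of the CAFS test, whatever covariance %SVC uses. A breach through H02 needs a false H01 that is found significant, a true null for %SVC, non-convergence, and a slope-type covariance.

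**The case against.** The strongest reply is that this is a pre-specified, ordered fallback for an event that will probably not happen. Six visits and about 380 subjects are comfortable for an unstructured matrix. The documents give no probability of failure and no covariance for %SVC, so any error rate is conditional on assumptions from outside them. All of that stands, and it sets the severity.

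Three stronger readings are tempting, and the documents support none of them:

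- *The fallback understates the standard error, so H02 runs at about 6–10%.* The direction depends on the true correlation: exponential decay makes the test conservative. The range also merges two events, since values near 8–11% need Toeplitz, hence failure of compound symmetry too, together with strong slope variation.
- *The 5% family-wise error is broken.* The H01 gate confines any breach to the narrow combination in step 5.
- *Every endpoint that reuses the model is affected.* ALSAQ40 and %FVC cannot be, so H03 is untouched by this mechanism.

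It is also fair to object that sandwich errors repair only the standard error. With dropout at random, a wrong covariance can bias the Week 48 estimate as well.

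What remains is that variable slopes are a reasonable expectation in a trial that stratifies on screening rate of decline, and that a pre-specified procedure should hold its level in the branch where it is used.

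**Conclusion.** The concern holds in a limited form. If the unstructured model for %SVC does not converge, the fallback in SAP 9.2.1.4.1 gives a Week 48 test whose level is not assured. Assuming slopes vary between patients, it is about 5–7% under heterogeneous compound symmetry and about 5–11% under heterogeneous Toeplitz. With exponentially decaying correlation it is about 4–5% and 3–3.5% (2.6% in one simulation).

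These ranges rest on assumed slope and error variances, 30% dropout, and an approximation to Kenward-Roger. ALSFRS-R change and body weight are exposed in the same way, but without a confirmatory consequence. Severity is low: the trigger is unlikely, and H02 is reached only after a significant H01.

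**What to change.** Amend SAP 9.2.1.4.1 before database lock; the models that refer to it inherit the change.

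1. On non-convergence, first refit the same unstructured matrix with a Cholesky parameterisation (TYPE=FA0(6) in PROC MIXED) or better starting values. This comes first because it keeps the intended model and so avoids both the wrong standard error and any bias from a wrong covariance.
2. If a structured covariance is still needed, take the Week 48 contrast with empirical (sandwich) standard errors. In the large-sample calculation this restores 5.0%. In random-slope simulations with 190 per arm (800 runs per scenario) it gave 4.1–5.9%.

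The cost is about one sentence and one SAS option. Kenward-Roger degrees of freedom are lost in step 2, which matters little at about 380 subjects, and step 2 does not remove bias in the estimate. Choosing a remedy only after seeing the fit fail would be post hoc.
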